In the open-label study, participants' Children's Depression Rating Scale (CDRS-R) scores were reduced by 44% [55]. Moreover, utilizing pre- and post-treatment brain scans we found that brain PCr concentrations increased with eight weeks of creatine supplementation when compared to a comparison group of non-depressed adolescent controls [55]. In the dose-ranging study, participants were randomly assigned to treatment from one of the four study drug groups for 8 weeks. Participants randomized to all creatine treatment groups showed greater decreases in CDRS-R scores, with reductions between 28-42%, compared to the CDRS-R scores of participants randomized to placebo, who showed a decrease of 24% [unpublished data]. Participants treated with 10g daily creatine showed the highest increases in frontal lobe PCr, and were the only participants showing post-treatment increases in frontal lobe beta-NTP. In both studies, creatine was well-tolerated, and participants experienced no suicide attempts or psychiatric hospitalizations over the 8-week trial. We observed no persistent or clinically significant abnormalities on serum or urine laboratory tests.

The neuroimaging and clinical results from the R21 study suggest that daily adjunctive treatment of 10g creatine is associated with the greatest change in PCr, and higher PCr is associated with lower depression scores. Therefore, the dose of creatine our data suggests is most likely to engage the neurochemical target is the 10g dose. At the same time, our data do not suggest that the 10g dose poses significantly greater risks to subjects compared with placebo, other than weight gain attributable to intracellular water.

The current protocol seeks to expand upon our previous work by opening recruitment on a pilot study of creatine 10g daily vs. placebo as a treatment for female adolescents with SSRI-resistant MDD. The purpose of the pilot study is twofold: A) to evaluate several aspects of the feasibility of creatine supplementation as a treatment for this population; and B) to estimate the

effect size of adjunctive creatine, to inform the design and implementation of a potential future efficacy trial.

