Sakellaris has studied creatine supplementation to prevent complications of Traumatic Brain Injury (TBI) in children [124, 125]. The study randomized 39 patients between 1 and 18 years of age with TBI to treatment with 0.4 gm/kg of body weight per day, or to treatment as usual for six months. The authors found no evidence of hepatic, renal, or cardiac toxicity in the patients who received creatine [124]. There was no increased incidence of intracranial events or medical complications observed in the patients receiving creatine [124]. The investigators concluded that no side effects were observed due to creatine administration [125]. Interestingly, there was a significant difference between the creatine-treated group and the control group on the TBI sequela of "Fatigue" ($p < 0.001$). Specifically, the proportion of children who reported experiencing "No Fatigue" 6 months after their TBI was significantly higher in creatine-treated participants than in controls (88.9% vs. 17.6%). This is notable because "Fatigue or loss of energy" is one of the diagnostic criteria for Major Depressive Disorder [126].

The Cooperative International Neuromuscular Research Group conducted a randomized placebo-controlled trial that enrolled 50 children between the ages of 4 and 10 years with Duchenne Muscular Dystrophy. The study was a 3-arm trial: placebo vs. creatine vs. glutamine [127]. Participants in the creatine group received 5 gm/day for six months. The research group reported that there were no significant differences in side effect profile among the three groups, and that creatine and glutamine were safe and well-tolerated over 6 months at the doses prescribed [127].

In summary, SSRI-resistant adolescent MDD is a public health problem that represents a significant unmet need. The dietary supplement creatine is a hypothesis-driven SSRI augmentation strategy, and measurement of PCr with ^{31}P -MRS has the potential to serve as a translational biomarker of juvenile MDD pathophysiology and treatment response. Creatine has been studied as a treatment for numerous pediatric central nervous system disorders, but its

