use in child psychiatry is novel. Creatine's gender-specific effects in animal models mandate that studies in youth be initially limited to female participants. Expanding upon our group's recent completion of a multidose study to establish which of four daily creatine doses offers the best combination of efficacy, safety and tolerability in adolescent females with SSRI-resistant MDD, we propose to conduct a pilot, placebo-controlled study of 10g daily adjunctive creatine, the dose selected from the dose-ranging trial, for adolescent females with SSRI-resistant MDD. We propose to examine the relationship between depression severity and cerebral PCr and to measure the effect size of adjunctive creatine vs. placebo on brain chemistry and clinical outcome in adolescent females with SSRI-resistant MDD.

OBJECTIVES:

The primary hypothesis is that compared to placebo, 10g of daily creatine monohydrate for eight weeks will be associated with significant increases in frontal lobe PCr and β -NTP concentrations. A secondary hypothesis is that decreased depressive symptoms measured with the CDRS-R and Montgomery Asberg Depression Rating Scale (MADRS) will be reciprocally correlated with increased β -NTP concentrations.

PARTICIPANT SELECTION CRITERIA:

Thirty-three female adolescents with MDD will be randomly assigned in a 1:1 ratio to either treatment for eight weeks, for a total of 66 MDD participants. Additionally, 40 healthy adolescents will be recruited as comparison subjects for the study. Key inclusion, exclusion, and study withdrawal criteria for each subject group are summarized below.

MDD SUBJECTS

Inclusion Criteria:

- Participants must be female.
- Participants must be able to grant informed consent (age ≥ 18), or parent/guardian permission plus participant assent (age < 18).
- Participants must meet DSM-IV criteria for MDD, with current mood state depressed for > 2 weeks.
- Participants must be between the ages of 12 and 21.
- Current CDRS-R raw score of ≥ 40 or MADRS score ≥ 25 ; and CGI-S score ≥ 4 .
- Participants may be enrolled in individual and/or group psychotherapy, if it has been ongoing for at least 8 weeks.

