We hypothesize that at baseline, CDRS-R scores are negatively correlated with cerebral PCr in female adolescents with SSRI-resistant MDD. We also hypothesize that for participants whose MDD responds to creatine, change CDRS-R score will be inversely correlated with change in brain beta-NTP levels (i.e. participants who have a significant decrease in their CDRS-R score will show an increase in beta-NTP).

Both intent-to-treat (ITT; encompasses all participants who receive >1 dose of study drug) and protocol completer analyses will be performed. A participant completing 8 weeks of treatment and both ^{31}P -MRS scans will be considered a "completer." Data will be expressed as mean + standard deviation (SD). Group differences in demographic variables involving continuous data will be calculated using one-way analysis of variance. Between-group comparisons involving categorical variables will be assessed using Fisher's exact test for n x k contingency tables. A linear mixed model (LMM) will be used to account for the association between measurements (baseline and post-treatment) for each individual for the repeated measures analysis. Exploratory data analysis using non-parametric statistical tests (e.g., Wilcoxon Rank-Sum test and the Mann-Whitney U-test) will also be performed. Statistical significance will be defined at the two-tailed, 0.05 level. Stata 11 (StataCorp LP, College Station, TX) and SAS 9.2 (SAS Institute, Cary, NC) software will be used for statistical calculations. Confidence intervals for all estimated parameters will be constructed using a 95% level.

Power Analysis and Sample Size Calculations: Calculations are based on the open-label female adolescent SSRI-resistant MDD creatine data obtained at our site, and our adult creatine studies. All power calculations are two-tailed with an alpha level of 0.05, and were performed in the specialized software PASS (NCSS, Kaysville, UT). The minimum required sample size

satisfying our hypothesis is 30 creatine-treated, 30 placebo-treated, and 30 age-matched healthy controls. Assuming a 10% attrition rate for MDD subjects and a 30% attrition rate for healthy controls, we propose to enroll a total of 66 female adolescents with SSRI-resistant MDD and 40 healthy controls. The central hypothesis and power analysis for the R33 clinical trial are described below.

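### The rationale rests largely on PCr, but the only prespecified link between metabolite change and symptom change is for beta-NTP, so any PCr-change link would be post hoc

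*Combined protocol and SAP*

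**What the plan says.** **Rationale.** In the Background section on antidepressant effects in females, the R21 dose-ranging results are summarised by saying that "10g creatine is associated with the greatest change in PCr, and higher PCr is associated with lower depression scores". The same section reports that participants on 10 g "were the only participants showing post-treatment increases in frontal lobe beta-NTP". The summary closing the paediatric safety section says that measuring PCr by 31P-MRS "has the potential to serve as a translational biomarker of juvenile MDD pathophysiology and treatment response".

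**Aims and hypotheses.** Just before the Objectives, the plan states: "We propose to examine the relationship between depression severity and cerebral PCr". It gives no time point, change score or model. The primary hypothesis in the Objectives is that "10g of daily creatine monohydrate for eight weeks will be associated with significant increases in frontal lobe PCr" and beta-NTP, compared with placebo. The secondary hypothesis is that falls in CDRS-R and MADRS "will be reciprocally correlated with increased β -NTP concentrations". PCr does not appear in it.

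**Analyses.** The Statistical Analyses section has two hypotheses relating symptoms to metabolites:
- At baseline: "We hypothesize that at baseline, CDRS-R scores are negatively correlated with cerebral PCr in female adolescents with SSRI-resistant MDD".
- For change, restricted to participants whose depression responds to creatine: "change CDRS-R score will be inversely correlated with change in brain beta-NTP levels".

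No model is named for either correlation, and response is not given a threshold.

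**The concern.** The argument for the trial has three steps: creatine raises PCr, PCr is related to depression severity, and PCr may therefore mark treatment response. The first step is tested by the primary hypothesis. The second is carried forward as a correlation taken before any study drug. The third, whether participants whose PCr rises also improve, has no prespecified analysis.

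The question would then be answered, if at all, after the data are seen, with two metabolites, two symptom scales and several possible populations to choose from. A link found that way is weak evidence, and the absence of a reported link is hard to interpret. This matters for a pilot that is meant to estimate effect sizes for a possible later efficacy trial.

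The programme's open-label data sharpen the point. The Power Analysis section reports that PCr rose and beta-NTP fell after creatine augmentation, and the Background reports that CDRS-R fell by 44% in that study. At group level, beta-NTP moved against the direction of the planned symptom link, while PCr moved as the rationale would predict.

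**Working it through.** **1. Where each metabolite meets symptoms.**

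| Place | Metabolite | Symptom quantity | Population |
|---|---|---|---|
| General aim before the Objectives | PCr | Severity, time point not stated | Adolescent females with SSRI-resistant MDD |
| Objectives, secondary hypothesis | beta-NTP | Decrease in CDRS-R and MADRS | Not stated |
| Statistical Analyses, first hypothesis | PCr | CDRS-R at baseline | SSRI-resistant MDD |
| Statistical Analyses, second hypothesis | beta-NTP | Change in CDRS-R | Creatine responders |

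No row pairs PCr change with symptom change. A pre-treatment correlation contains no response to treatment and cannot fill that gap.

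**2. Are the data collected?** Yes. Table 1 places the MDD scans at Weeks 0 and 8, and I read its rating-scale row as covering both visits. The gap is one of specification.

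**3. The plan's own power figure.** The plan gives no power for any correlation. Its 86% is for the creatine versus placebo difference in metabolite change (d = 0.9, 30 per group, two-sided 0.05). With those inputs the noncentrality is 0.9 × √(30/2) = 3.49 on 58 df, and power is 92.9% (noncentral t). The stated 86% is not reproduced, but that is a separate matter on which nothing here depends.

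**4. What the missing analysis could show.** Inputs:
- n = 60 with both scans: the stated minimum of 30 + 30, close to 66 × 0.90 = 59.4 after the assumed 10% attrition.
- Two-sided alpha 0.05.
- One covariate (arm). Here r is the partial correlation of PCr change with symptom change given arm. Its values are illustrative, since the documents give none.

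Formula: z = atanh(r) × √(n − 3 − 1) = atanh(r) × √56 = atanh(r) × 7.483; power ≈ Φ(z − 1.960).
- |r| = 0.30: 0.3095 × 7.483 = 2.316; Φ(0.356) = 0.64.
- |r| = 0.36: 0.3769 × 7.483 = 2.820; Φ(0.860) = 0.805, about 80%.
- |r| = 0.40: 0.4236 × 7.483 = 3.170; Φ(1.210) = 0.89.
- 95% CI at r = 0.30: 0.3095 ± 1.960/7.483 = 0.3095 ± 0.2619, which back-transforms to 0.05 to 0.52.

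**5. Effect of restricting to responders.** Without a covariate, the smallest |r| detectable with 80% power is tanh(2.802/√(n − 3)).
- All 30 in the creatine arm: tanh(2.802/√27) = 0.49.
- Assumed 18 responders: tanh(2.802/√15) = 0.62.
- Assumed 12 responders: tanh(2.802/√9) = 0.73.

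The documents give no responder count; 12 to 18 of 30 is my assumption. Selecting on the outcome also narrows the range of symptom change within the subgroup.

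**The case against.** The strongest defence is that beta-NTP is a reasonable symptom correlate. Only the 10 g group showed a beta-NTP rise in the dose-ranging study. The Background also describes an adult MDD pattern of low beta-NTP with high PCr, read as energy stores that cannot be used, so rising beta-NTP could plausibly mark recovery. This stands. It is a reason to test both metabolites and does not explain leaving out the one that the dose rationale ties to depression scores.

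It can also be said that the rationale speaks of PCr levels and not PCr change, so the baseline correlation does carry it forward. That is fair for the level association. It does not reach the treatment-response claim.

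Stronger conclusions that a reader might draw are not supported:
- *A PCr result cannot be linked to benefit.* It can be, from data already scheduled. The link is simply not prespecified.
- *A null beta-NTP correlation would refute the energy mechanism.* Treatment effects on both metabolites are still tested under the primary hypothesis.
- *The open-label data predict that the beta-NTP link will fail.* Opposite movements of group means do not fix the sign of a correlation within participants.
- *The severity entry rule cripples the baseline correlation.* That hypothesis is stated for the enrolled population, the rule accepts either a CDRS-R or a MADRS threshold, and the documents give no figure from which to size any attenuation.

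**Conclusion.** The gap is real but limited. The dose and biomarker rationale rests largely on PCr, and PCr is part of the primary hypothesis, but the plan prespecifies a symptom-change correlation only for beta-NTP and, in the Statistical Analyses section, only among creatine responders. The primary comparison, sample size and data collection are unaffected.

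The added analysis would be informative without being decisive: about 64% power at |r| = 0.30, 80% at |r| = 0.36, and an interval of roughly 0.05 to 0.52 around an observed 0.30. These figures assume about 60 complete pairs, approximate bivariate normality given arm, and a similar slope in both arms. Even a clear association would not show that raising PCr causes improvement, because PCr change is not randomised within arm.

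**What to change.** In the Objectives and the Statistical Analyses section:

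1. Add a secondary analysis in all randomised MDD participants with both scans. Regress change in CDRS-R (Week 8 minus baseline) on change in frontal PCr, with treatment arm in the model. Repeat separately for MADRS. Report each estimate with its 95% CI. The arm term is needed because otherwise a treatment effect on both quantities would produce a pooled correlation by itself.
2. Fit the same stated model for beta-NTP in all such participants, replacing the responders-only restriction. The section currently states no model or arm adjustment for that correlation, so the model has to be written out in full.
3. Label these analyses secondary and associational, not proof of mediation.
4. State that the baseline CDRS-R/PCr correlation will not be cited as evidence about treatment response.

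The cost is a few lines of text and one more secondary estimate per scale, with no new data. To keep the choice independent of the results, make the change before the blind is broken.

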The hypothesis that PCr and beta-NTP levels measured with 31P-MRS will show significant change associated with 8 weeks of 10g daily creatine compared with placebo in female adolescents with SSRI-resistant MDD evaluates the significance of treatment-related recovery. In our open-label creatine data, we found that female adolescents with SSRI-resistant MDD showed increased PCr and decreased beta-NTP following creatine augmentation. The effect size of these changes were estimated to be approximately 1.0 (Cohen's d) with 10% SD. Therefore, when we conservatively set the effect size to be 0.9; sample size of 30 per each group; and common SD within a group of 10%, the changes of metabolite levels between creatine and placebo groups will be significantly (alpha level of 0.05) detectable with 86% of power.

ADMINISTRATIVE RESPONSIBILITIES

Resources:

The Brain Institute

The facilities at the University of Utah that are available for the proposed research include the following: the Brain Institute and UNI. The Brain Institute currently occupies 5,900 square feet of office and laboratory space in a building in the University of Utah Research Park adjacent to the Health Sciences campus. It also occupies clinical space in UNI, the site of the Brain Institute's Siemens 3T MRI research scanner.

Recruitment of Participants:

- No “cold calls” will be made by members of the study team.
- An informational flyer will be placed (with permission) on public bulletin boards. The flyer will be submitted to the IRB for approval prior to posting. Examples of public bulletin boards may include but are not limited to: University of Utah bulletin boards (for example, the Health Science Education Building, the College of Nursing, the Department of Psychology, etc.), the Salt Lake Community College, and business frequented by adolescents and their parents.
- An informational brochure has been created, to be displayed (with permission) in appropriate public areas, and to be provided to practicing mental health clinicians, pediatricians and family practitioners in the Salt Lake City area. The clinicians, at their sole discretion and without compensation, will pass the brochure to the parent(s) or guardian(s) of adolescent clients in cases where they deem it appropriate. The brochure will be submitted to the IRB for approval, prior to distribution to clinicians.

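### The secondary symptom/beta-NTP correlation has two different populations in the plan, and neither version soundly tests whether beta-NTP change tracks improvement among participants

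*Combined protocol and SAP*

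**What the plan says.** The hypothesis appears twice.

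- **OBJECTIVES.** The secondary hypothesis is that "decreased depressive symptoms measured with the CDRS-R and Montgomery Asberg Depression Rating Scale (MADRS) will be reciprocally correlated" with increased beta-NTP. It covers both scales. It names no analysis population, correlation method, covariates or arm term.
- **Statistical Analyses.** The hypothesis becomes: "for participants whose MDD responds to creatine, change CDRS-R score will be inversely correlated with change in brain beta-NTP levels". This covers CDRS-R only and confines the analysis to creatine responders. A gloss in parentheses puts it at participant level: those whose CDRS-R falls significantly are expected to show a rise in beta-NTP. Response is not defined.

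The only model named in Statistical Analyses is general: "A linear mixed model (LMM) will be used to account for the association between measurements (baseline and post-treatment) for each individual". It is not tied to the correlation, and no arm term is stated. The two analysis sets defined there, intent-to-treat and completers, both contain both arms.

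The documents also disagree on which way beta-NTP moves. Power Analysis and Sample Size Calculations reports that beta-NTP decreased in the open-label creatine data. The background section on antidepressant effects in females reports an increase in frontal beta-NTP at 10 g in the dose-ranging study. The primary hypothesis expects an increase.

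**The concern.** The question of interest is whether participants whose beta-NTP changes more also improve more. Neither version answers it cleanly.

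In the OBJECTIVES version, nothing prevents pooling the two arms. The trial expects creatine to change beta-NTP and hopes it lowers symptom scores. If both happen, arm is a common cause of both changes, and the pooled correlation partly restates the two treatment effects. A significant result could then be taken as individual-level tracking when there is none within either arm.

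In the Statistical Analyses version, arm is constant, so that artefact cannot arise. But the participants are chosen by their symptom outcome, which is one of the two variables being correlated. That narrows its range, weakens any true correlation and leaves few participants. Without placebo participants, a link specific to creatine cannot be told from one that accompanies recovery in general.

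At stake is how a pilot result on the metabolite and symptom relationship would be read when the next trial is designed.

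**Working it through.** **Inputs from the documents.** Arm effect on metabolites d1: "conservatively set the effect size to be 0.9". Analysed size: "sample size of 30 per each group", so 60 in total with 1:1 allocation. Two-sided alpha 0.05.

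**Input assumed.** Arm effect on symptoms, d2. The background gives CDRS-R falls of 28-42% on creatine and 24% on placebo, without SDs, so d2 cannot be derived. I use 0.2 to 0.8.

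**The plan's own figure.** No power or effect size is given for the correlation. The 86% power concerns the between-arm metabolite comparison. At d = 0.9 and 30 per group a two-sided t test has 92.9% power, so 86% does not reproduce. That is a separate matter: only d and n are used here.

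**Pooled version, no link within either arm.** With within-arm SDs of 1 and equal arms, the between-arm covariance is -d1 × d2/4 and the pooled variances are 1 + d1²/4 and 1 + d2²/4. Hence

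r = -d1 × d2 / sqrt((d1² + 4)(d2² + 4)).

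For d1 = 0.9 and d2 = 0.5: -0.45 / sqrt(4.81 × 4.25) = -0.45/4.52 = -0.10.

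Simulation (40,000 trials per setting, 30 per arm, zero within-arm correlation):

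| Assumed symptom d2 | Pooled r | Rejection, pooled | Rejection, arm-adjusted |
|---|---|---|---|
| 0.2 | -0.04 | about 6% | about 5% |
| 0.3 | -0.06 | 7 to 8% | about 5% |
| 0.5 | -0.10 | about 12% | about 5% |
| 0.8 | -0.15 | about 22% | about 5% |

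The critical |r| at n = 60 is 0.254, so the induced correlation is usually not significant. Its effect is a raised error rate. If beta-NTP falls by the same amount, r has the same size with a positive sign and total rejection is about the same. Pooling could then wrongly count against the hypothesis.

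**Responder-only version, no link.** Taking the best half of the creatine arm by symptom change as a stand-in for responders, rejection is 4.9-5.3%. There is no arm artefact.

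**Responder-only version, real link.** Assume a true within-arm r of -0.4.

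- Keeping the best half of a normal outcome leaves a fraction 1 - 2/π = 0.363 of its variance, so the SD ratio is u = 0.603.
- The correlation becomes r × u / sqrt(1 - r² + r² × u²) = -0.241 / sqrt(0.84 + 0.058) = -0.25.
- In simulation, 12 to 18 responders give a mean r of about -0.23 to -0.27, with 12-20% power.
- The arm-adjusted analysis of all 60 gives a mean r of about -0.40, with 89% power.

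**What the adjusted analysis can detect.** By Fisher's z, 80% power needs |r| = tanh((1.96 + 0.84)/sqrt(n - 3 - k)), with k covariates. For 60 participants and k = 1: tanh(2.80/sqrt(56)) = 0.36. For the creatine arm alone (n = 30, k = 0): tanh(2.80/sqrt(27)) = 0.49.

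**The case against.** The strongest reply is that the only version in the analysis section is restricted to creatine responders, where arm cannot create a correlation, and that OBJECTIVES is one sentence which never says the arms will be pooled. This stands in part. A reader might infer that an unadjusted pooled test is planned. The documents do not establish that; they leave the population open in one place and restrict it in another. But the restriction does not settle the matter. It leaves MADRS with only the OBJECTIVES wording, gives no rule for response, and brings the selection problem shown above.

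A reader might also infer that a spurious correlation will appear. It can appear, but at the assumed effects the pooled test is non-significant in about 78% to 94% of trials, and at a symptom effect of 0.2 or 0.3 SD the inflation is slight. Nor would the artefact necessarily favour the hypothesis, because the documents disagree on the direction of beta-NTP change.

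Finally, a reader might infer that the plan presents beta-NTP change as a biomarker of response. The statement that a measurement "has the potential to serve as a translational biomarker of juvenile MDD pathophysiology and treatment response", in the summary closing the paediatric safety review, is about PCr. It does not support that reading of beta-NTP. The relevant text is the participant-level gloss in Statistical Analyses.

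That this is a secondary hypothesis in a self-described pilot also stands, and it limits the weight of the point.

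**Conclusion.** The concern holds as a point about an under-specified and internally inconsistent secondary analysis. OBJECTIVES and Statistical Analyses give different populations and different scales for one hypothesis, and neither version is a sound test of tracking among participants within an arm.

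If the arms were pooled without adjustment, the 5% error rate would become about 6% to 22%. That rests on the planned metabolite effect of 0.9 SD, 30 per arm, zero within-arm correlation and an assumed symptom effect of 0.2 to 0.8 SD. If only creatine responders were analysed, the error rate would hold, but a true r of -0.4 would shrink to about -0.23 to -0.27 with 12-20% power, against 89% for the adjusted analysis. That rests on the assumed r and on 12 to 18 responders chosen by symptom change.

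The plan should be changed. The primary comparison is unaffected.

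**What to change.** Reconcile OBJECTIVES and Statistical Analyses so that they state one hypothesis, one population and one method for both scales. Suggested content:

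- **Population:** all randomised participants with both scans, with no selection on response.
- **Model:** regress Week 8 CDRS-R on change in beta-NTP, with treatment arm and baseline CDRS-R as covariates. Fit the same model separately for MADRS with its own baseline.
- **Report:** the arm-adjusted partial correlation with 95% CI, and the estimate within each arm.
- **Interpretation:** label the analysis exploratory, and do not read an unadjusted pooled correlation as individual-level tracking.
- **Direction:** reconcile the two statements on how beta-NTP moved in the earlier studies, so that the expected sign is clear.

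The cost is one degree of freedom for arm (plus one for the baseline score) and a sentence of SAP wording. No new data are needed: Table 1 already schedules scans and both scales at Weeks 0 and 8 for all MDD participants.
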